14.5 Confidentiality

Information about study subjects will be kept confidential and managed according to the requirements of the Health Insurance Portability and Accountability Act (HIPAA). Those regulations require a signed subject authorization informing the subject of the following:

- What protected health information (PHI) will be collected from subjects in this study
- Who will have access to that information and why
- Who will use or disclose that information

In the event that a subject revokes authorization to collect or use PHI, the investigator, by regulation, retains the ability to use all information collected prior to the revocation of subject authorization. For subjects that have revoked authorization to collect or use PHI, attempts should be made to obtain permission to collect at least vital status (e.g., that the subject is alive) at the end of their scheduled study period.

The subject binders will be maintained with in the CPDM offices, a secured floor within the Herbert Irving Pavilion and only the investigator and study staff will have access to the file.

14.6 Source Documents

Source data is all information, original records of clinical findings, observations, or other activities in a clinical trial necessary for the reconstruction and evaluation of the trial. Source data are contained in source documents Examples of these original documents, and data records include: hospital records, clinical and office charts, laboratory notes, memoranda, subjects' diaries or evaluation checklists, pharmacy dispensing records, recorded data from automated instruments, copies or transcriptions certified after verification as being accurate and complete, microfiches, photographic negatives, microfilm or magnetic media, x-rays, subject files, and records kept at the pharmacy, at the laboratories, and at medico-technical departments involved in the clinical trial.

14.7 Case Report Forms

The study case report form (CRF) is the primary data collection instrument for the study. All data requested on the CRF must be recorded. All missing data must be explained. If a space on the CRF is left blank because the procedure was not done or the question was not asked, write "N/D". If the item is not applicable to the individual case, write "N/A".

14.8 Records Retention

Records relating to a specific research activity, including research records collected by investigators, must be maintained for at least three years after completion of the research (45 CFR 46.115(b); 21 CFR 56.115(b); 21 CFR 312.62). This minimum retention period applies whether or not any subjects were enrolled in the study. If the research is FDA regulated, records should be retained for at least two years after approval of the investigational agent by FDA; if it is not approved, records should be retained at least two years after the study is terminated and FDA is notified (note the additional requirement below for clinical research studies); Clinical records, including consent forms that document clinical intervention or clinical diagnostic procedure research-related procedures, must be retained in medical records by the institution for at least seven years, per CUMC and NYP policy which is based on state law.

15. STATISTICAL PLAN

15.1 Primary Endpoint

The primary endpoint is the progression free rate at 12 weeks (PFR₁₂). This corresponds to the number of patients who are alive and without evidence of disease progression at 12 weeks out of all evaluable patients.

Two recent randomized phase 3 studies evaluated novel agents (trabectedin, eribulin) in a population of patients with LPS and LMS. In both studies, the cytotoxic agent dacarbazine was used as the active comparator/control arm. Dacarbazine is a chemotherapy agent often used for later-line treatment of soft tissue sarcoma, including LPS and LMS.

In the randomized study of trabectedin versus dacarbazine in patients with LPS and LMS (n=518), median PFS was 4.2 months versus 1.5 months, and the progression-free rate at 3 months (12 weeks) was 56% versus 34%, respectively[1]. In a subset analysis, outcomes were similar in LPS and LMS. Similarly, in the randomized study of eribulin versus dacarbazine (n=452), the median PFS was 2.6 months versus 2.6 months, and the progression-free rate at 3 months (12 weeks) was 33% versus 29%.[2]

Based upon the results of these studies, a $PFR_{12} \le 30\%$ would be considered inactive and unworthy of further study, whereas a $PFR_{12} \ge 55\%$ would suggest clinically meaningful activity, worthy of further evaluation in subsequent studies.

A Simon optimal 2-stage design is used. The study will enroll 10 patients with LMS and LPS in the first stage. If 4 or more patients meet the PFR_{12} endpoint in the first stage (4/10), the study will proceed to the second stage, enrolling an additional 24 patients for a total sample size of 34 patients. If 15 or more total patients meet the PFR_{12} endpoint in the overall study population (15/34), the agent will be considered promising and worthy of further study.

An interim analysis will be performed after the first stage is completed. In the event that the study meets the stage 1 endpoint, but all patients who meet the PFR_{12} endpoint are of the same histology (either LMS or LPS), then the study will proceed to full accrual in that respective histology only. In this event, no further patients will be enrolled from the histology in which no patients met the PFR_{12} endpoint during stage 1.

This design provides 85% power and type 1 error (1-sided) of 0.05 to evaluate for an improvement in PFR_{12} from $\leq 30\%$ to $\geq 55\%$.

For the first stage of enrollment, among the 10 patients enrolled, 5 patients will have LMS, and 5 patients will have LPS. If the study proceeds to the second stage, among the 12 patients subsequently enrolled, 12 patients will have LMS and 12 patients will have LPS.

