4.2 Safety Lead-In

Recognizing the limited clinical experience with ATX-101, we will perform a safety lead-in among the first 10 patients enrolled and treated on the study to confirm the safety and tolerability of the proposed dose and schedule. The safety lead-in will apply to the first 10 patients treated for two cycles (6 weeks). These patients will undergo safety assessments as specified in the study calendar.

The study will not proceed to further accrual until these 10 patients have completed two cycles or 6 weeks of study treatment; however, patients who end study treatment during this period for reasons other than toxicity, i.e., disease progression, will not be replaced. After 10 patients complete 2 cycles of treatment, the study investigators will review the safety data. If 3 or more patients in the safety lead-in population experience DLTs as defined below, the study team will consider terminating the study or amending the study to evaluate an alternative dose and schedule. In addition, if 2 or more events of grade 4 infusion related reaction occur, the study team will also consider terminating the study. Formal documentation of the study team's review of toxicity data from the safety lead-in will be provided to the IRB and FDA prior to resuming accrual.

The following definitions of dose-limiting toxicity (DLT) apply to the safety lead-in. DLTs are defined as the following toxicities which are attributed as at least possibly related to the study drug and not to disease, and which occur (or first become evident) during a prespecified timeframe. For the purposes of the safety lead-in, this timeframe is the first two cycles of treatment.

- Any grade ≥3 non-hematologic toxicity, except grade ≥3 fatigue, nausea, or vomiting which must persist >5 days despite maximal supportive care to be considered dose limiting. This includes any grade 3 or 4 infusion-related reaction.
- 2. Any grade \geq 4 hematologic toxicity lasting >14 days, except grade 4 lymphopenia, which is not considered a DLT.
- 3. Grade \geq 3 neutropenia with fever
- 4. Grade \geq 3 thrombocytopenia with clinically significant bleeding.
- 5. Any laboratory abnormality not otherwise addressed above which is both associated with clinical sequelae and which fails to resolve to grade ≤1 within 5 days of occurrence, or any laboratory criteria meeting Hey's law for liver toxicity.

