11. STUDY CALENDAR

CBC w/differential (1,3)*	Х	Х	Х	Х	Х		Х		Х
Comprehensive metabolic panel (1,3,4)*	Х	Х	Х	Х	Х		Х		Х
Serum or urine pregnancy test (1, 3)	Х								Х
Urinalysis (1, 3)	Х						Х		Х
CT or MRI of chest, abdomen, pelvis (2)	Х						Х		Х
Tumor biopsy for correlative studies (5)	Х				X				
Follow-up telephone contact (6)	llow-up telephone contact (6)				Х				
*Clinical/laboratory safety assessm	ents must	be con	nple	ted w	ithin 24	4 hours	prior to	treatmen	t.

(1) Screening procedures must be completed within 21 days of initiating study treatment, with the exception of the serum or urine pregnancy test, which must be completed within 7 days of initiating study treatment. Protocol-specified screening procedures that are performed as part of standard of care and are within the specified timeframes may be used for screening purposes.

(2) Baseline imaging can include either (a) CT, spiral CT or MRI, or (b) FDG-PET with diagnostic CT performed with IV and oral contrast and CT acquired with 5 mm or less slice thickness. Imaging studies used for baseline tumor measurements must be performed within 21 days of initiating study treatment. Imaging studies are performed every 2 cycles (6 weeks, 42 days) for the first 36 weeks of study treatment, and then every 3 cycles (9 weeks, 63 days) thereafter. Imaging studies may be performed +/- 5 days from the required date. In the event of dose delays/holds, imaging studies should still be obtained at the scheduled timepoints as measured from cycle 1 day 1, without delays to account for dose delays/holds. Confirmatory scans must be obtained at least 4 weeks after the documentation of an objective response. It is acceptable to perform confirmatory assessments at the next appointed evaluation per protocol. Response assessment should include assessment of all sites of disease and use the same imaging method as used at baseline whenever possible.

(3) All laboratory studies may be performed +/- 3 days from the required date. Local laboratory testing is permitted, except for the serum/urine pregnancy test.

(4) Comprehensive metabolic panel includes albumin, alkaline phosphatase, total bilirubin, bicarbonate, blood urea nitrogen, calcium, chloride, creatinine, glucose, potassium, total protein, AST, ALT and sodium.

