12.1.1 Definitions

Evaluable for toxicity: All patients will be evaluable for toxicity from the time of their first treatment with ATX-101. The safety population will consist of all patients who received at least one dose of study drug.

Evaluable for objective response: Only those patients who have measurable disease present at baseline, have received at least one cycle of therapy, and have had their disease re-evaluated will be considered evaluable for response. These patients will have their response classified according to the definitions stated below. (Note: Patients who exhibit objective disease progression prior to the end of cycle 1 will also be considered evaluable.) Patients who end study treatment during cycle one of treatment may be replaced.

Evaluable Non-Target Disease Response: Patients who have lesions present at baseline that are evaluable but do not meet the definitions of measurable disease, have received at least one cycle of therapy, and have had their disease re-evaluated will be considered evaluable for non-target disease. The response assessment is based on the presence, absence, or unequivocal progression of the lesions.

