12.4.3 Evaluation of Best Overall Response

The best overall response is the best response recorded from the start of the treatment until disease progression/recurrence (taking as reference for progressive disease the smallest measurements recorded since the treatment started). The patient's best response assignment will depend on the achievement of both measurement and confirmation criteria.

Target Lesions	Non-Target Lesions	New Lesions	Overall Response	Best Overall Response when Confirmation is Required*
CR	CR	No	CR	≥4 wks. Confirmation**
CR	Non-CR/Non-PD	No	PR	
CR	Not evaluated	No	PR	≥ 4 wks.
PR	Non-CR/Non-PD/not evaluated	No	PR	Confirmation**
SD	Non-CR/Non-PD/not evaluated	No	SD	documented at least once ≥4 wks. from baseline**
PD	Any	Yes or No	PD	
Any	PD***	Yes or No	PD	no prior SD, PR or CR
Any	Any	Yes	PD	

* See RECIST 1.1 manuscript for further details on what is evidence of a new lesion.

** Only for non-randomized trials with response as primary endpoint.

*** In exceptional circumstances, unequivocal progression in non-target lesions may be accepted as disease progression.

Note: Patients with a global deterioration of health status requiring discontinuation of treatment without objective evidence of disease progression at that time should be reported as "symptomatic deterioration." Every effort should be made to document the objective progression even after discontinuation of treatment.

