15.6.2 Evaluation of response

All patients included in the study who receive at least one treatment with the study drug will be assessed for response to treatment, even if there are major protocol deviations or if they are ultimately deemed ineligible. Each patient will be assigned one of the following categories: 1) complete response, 2) partial response, 3) stable disease, 4) progressive disease, 5) early death from malignant disease, 6) early death from toxicity, 7) early death from other cause, or 9) unknown (not assessable or insufficient data).

16. **PROTECTION OF HUMAN SUBJECTS**

This study is to be conducted in accordance with applicable government regulations and Institutional research policies and procedures.

This protocol and any amendments will be submitted to a properly constituted Institutional Review Board (IRB), in agreement with local legal prescriptions, for formal approval of the study conduct. The decision of the IRB concerning the conduct of the study will be made in writing to the investigator and a copy of this decision will be obtained before commencement of this study.

All subjects for this study will be provided a consent form describing this study and providing sufficient information for subjects to make an informed decision about their participation in this study. This consent form will be submitted with the protocol for review and approval by the IRB for the study. The formal consent of a subject, using the IRB-approved consent form, must be obtained before that subject is submitted to any study procedure. This consent form must be signed by the subject or legally acceptable surrogate, as outlined in the IRB approved protocol, and the investigator-designated research professional obtaining the consent.

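### The PFR12 denominator is undefined; if the objective-response evaluability rule is applied to it, a cycle 1 failure can be replaced, and one such replacement in stage 2 lifts type I error from 4.6% to about 5.6%

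*Combined protocol and SAP*

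**What the plan says.** PFR12 is the primary endpoint and drives both decisions: at least 4 of 10 to continue, then at least 15 of 34 to call the drug promising. Section 15.1 counts patients "alive and without evidence of disease progression at 12 weeks out of all evaluable patients" and gives no definition of evaluable.

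The only efficacy definitions are in 12.1.1. Under the label for objective response, patients with measurable disease who "have received at least one cycle of therapy, and have had their disease re-evaluated will be considered evaluable for response". Two further sentences follow: "Patients who exhibit objective disease progression prior to the end of cycle 1 will also be considered evaluable", and "Patients who end study treatment during cycle one of treatment may be replaced". The second gives no limit on the reason for stopping.

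Other sections bear on the same patients:

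- Section 4.2, on the first 10 patients (who are also stage 1): "patients who end study treatment during this period for reasons other than toxicity, i.e., disease progression, will not be replaced".
- Section 15.6.2: "All patients included in the study who receive at least one treatment with the study drug will be assessed for response to treatment". It adds three early-death categories and one for unknown.
- Section 12.4.3 records decline without objective progression as symptomatic deterioration and adds: "Every effort should be made to document the objective progression even after discontinuation of treatment".
- Section 11, footnote 2: "Imaging studies are performed every 2 cycles (6 weeks, 42 days) for the first 36 weeks of study treatment". Cycles are 21 days, so cycle 1 ends three weeks before the first scheduled on-study scan.

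**The concern.** Two analysts following this protocol could reach different denominators. One would use 15.6.2 and keep every treated patient. The other would take evaluable from 12.1.1 and drop and replace a patient who left in cycle 1 without a re-evaluation.

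The sentence that keeps objective cycle 1 progressors evaluable gives limited protection, because no scan is scheduled until week 6. A patient who dies, declines clinically, withdraws or stops for toxicity in cycle 1 will usually have no scan. Those who die or decline are likely PFR12 failures. Replacing such a patient exchanges a failure for a new chance of success while the cut-offs stay fixed. The design has only 5.00 − 4.56 = 0.44 percentage points of room below its stated error limit. Replacement is also discretionary, in an open-label trial where the investigators see outcomes.

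**Working it through.** **Inputs (15.1).** Null 0.30, alternative 0.55; 10 patients in stage 1, continue at 4 or more; 24 more in stage 2, promising at 15 or more of 34; stated one-sided error 0.05 and power 85%.

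**Step 1: reproduce the plan.** P(promising) = Σ over x = 4 to 10 of P(X₁ = x) × P(X₂ ≥ 15 − x), with X₁ ~ Bin(10, p) and X₂ ~ Bin(24, p).

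| x | P(X₁ = x), p = 0.30 | P(X₂ ≥ 15 − x), n = 24 | Product |
|---|---|---|---|
| 4 | 0.2001 | 0.0742 | 0.0149 |
| 5 | 0.1029 | 0.1528 | 0.0157 |
| 6 | 0.0368 | 0.2750 | 0.0101 |
| 7 | 0.0090 | 0.4353 | 0.0039 |
| 8–10 | 0.0016 | – | 0.0010 |

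The sum is 0.0456. At p = 0.55 the same formula gives 0.8532. Both agree with the stated 5% limit and 85% power.

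**Step 2: replace would-be failures.** Replacing one stage 2 failure with a new patient is the same as treating 25 patients in stage 2 with the cut-offs unchanged. The second factor becomes P(Bin(25, 0.30) ≥ 15 − x) = 0.0978, 0.1894, 0.3231 and 0.4882 for x = 4 to 7. The products are 0.0196, 0.0195, 0.0119 and 0.0044, plus 0.0011 for x = 8 to 10, which sum to 0.0564 before rounding.

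| Replaced failures | Type I error, stage 2 | Type I error, stage 1 |
|---|---|---|
| 0 | 4.56% | 4.56% |
| 1 | 5.64% | 6.24% |
| 2 | 6.84% | 8.19% |

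Under 4.2 the stage 1 column is open only for patients who leave for toxicity.

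**Step 3: put a rate on it.** The documents give no early-exit rate. Assume that a fraction g of patients leave before week 12 unscanned, that a quarter of these leave in cycle 1, and that all would have failed. Following 4.2, replace cycle 1 leavers in stage 2 only. The null rate among counted stage 2 patients is then 0.30 / (1 − g/4), and stage 1 stays at 0.30.

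| g | Stage 2 null rate | Expected replacements, 24 × (g/4)/(1 − g/4) | Type I error |
|---|---|---|---|
| 5% | 0.3038 | 0.30 | 4.9% |
| 10% | 0.3077 | 0.62 | 5.2% |
| 15% | 0.3117 | 0.94 | 5.5% |

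**Step 4: two boundary cases.** If leaving is unrelated to outcome, a replacement has the same success probability as the patient who left, and the error stays at 4.56%. If 1, 2 or 3 stage 2 patients are omitted without replacement (n = 23, 22, 21, same cut-offs), the error falls to 3.6%, 2.8% or 2.1%. The excess therefore comes from replacing likely failures, not from leaving them out.

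**The case against.** The strongest reply is that 12.1.1 is headed for objective response, a secondary endpoint, and nothing in the protocol ties it to PFR12. Section 15.1 requires a patient to be alive, so a cycle 1 death is a failure without any scan. Section 7.3 lists clinical progression as its own reason to stop, so it can be read as evidence of progression. Section 15.6.2 sits inside the statistical plan and keeps every treated patient. Replacement is permitted, not required, and the sample size is fixed at 34. Sections 5.5.2 and 7.4 keep following patients who stop early, with disease status every three months for those who have not progressed.

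Most of this stands, and it rules out a stronger reading. A reader might infer that the plan requires early failures to be excluded, or that its type I error is 5.6% to 6.2%. The documents support neither. The 12.1.1 rule reaches PFR12 only by inference. The 6.2% figure needs a stage 1 replacement, which 4.2 rules out except for toxicity, and section 3.2 reports no dose-limiting toxicity and no related grade 3 or higher event in phase 1. At an assumed 5% removal with stage 2 replacement only, the error stays under 5%.

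What the reply does not do is settle the denominator. A death counts as a failure only if the patient is counted at all. Section 15.6.2 speaks of response categories and does not mention PFR12. The three-monthly follow-up specifies no scan, and 15.1 does not say how to score a patient without a week-12 assessment.

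**Conclusion.** The point holds as an undefined primary-endpoint denominator alongside a permissive replacement sentence that conflicts with 4.2 and 15.6.2. It is worth correcting because that sentence, if applied to PFR12, can bias the go/no-go decision. The size is modest and conditional: 5.6% for one would-be failure replaced in stage 2, 6.8% for two, and 4.9% to 5.5% under the assumed 5% to 15% removal. These figures assume that the replaced patients would all have failed and that the cut-offs stay at 4 and 15. With no replacement, or with leaving unrelated to outcome, there is no excess over 4.56%. The stated design figures themselves are correct.

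**What to change.** In 15.1, state that:

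- the PFR12 denominator is every patient who receives at least one dose, and no treated patient is replaced for PFR12;
- death, objective progression, or clinical progression or symptomatic deterioration before week 12 counts as not progression-free;
- a patient with no week-12 scan who is shown progression-free at a later scan counts as progression-free;
- any other patient without a week-12 assessment counts as not progression-free in the primary analysis, with a sensitivity analysis that excludes those who left for reasons unrelated to disease.

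In 12.1.1, state that the evaluability and replacement sentences do not apply to PFR12.

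The cost is a few sentences; sample size and cut-offs do not change. Type I error stays at or below 4.6%, because no treated patient's chance of counting as a success exceeds the true PFR12. The downside is power. If 5% of patients leave for unrelated reasons and cannot be assessed, the success rate under the alternative is 0.55 × 0.95 = 0.5225 and power is 78.5%; at 10% (0.495) it is 69.8%, and at 15% (0.4675) it is 59.3%. Power stays at 85.3% if the leavers would have failed anyway, or if they are all scanned at week 12.

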For the first stage of enrollment, among the 10 patients enrolled, 5 patients will have LMS, and 5 patients will have LPS. If the study proceeds to the second stage, among the 24 patients subsequently enrolled, 12 patients will have LMS and 12 patients will have LPS.	
--	--

[figure not shown]

Table of Contents

Protoc	ol Signature Page	5
Protoc	ol Synopsis	6
1.	INTRODUCTION AND RATIONALE	15
	1.1 Disease Background	15
	1.2 ATX-101, a peptide drug targeting PCNA	15

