4.3 Number of Patients

The study size is 34 patients.

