15.2 Size/Accrual Rate

The sample size is 34 patients. The planned accrual rate is 2-3 patients per month. Therefore, accrual is expected to be complete in no more than 17 months. Assuming patients continue treatment for up to 1 year (12 months) and allowing 6 months for quality assurance, the anticipated duration of the study is approximately 35 months.

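### The fixed 12 LMS + 12 LPS stage 2 split cannot be followed if one histology is closed after stage 1, and section 15.1 misprints the stage 2 total as 12

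*Combined protocol and SAP*

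**What the plan says.** Section 15.1 describes a Simon optimal two-stage design. Ten patients (5 LMS, 5 LPS) enter stage 1. With 4 or more successes on the 12-week progression-free rate, stage 2 opens, "enrolling an additional 24 patients for a total sample size of 34 patients". With 15 or more successes "in the overall study population (15/34), the agent will be considered promising and worthy of further study". The stated properties are 85% power and a one-sided type 1 error of 0.05 for 30% against 55%.

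A special branch applies if stage 1 passes but all its successes are in one histology: "then the study will proceed to full accrual in that respective histology only", and "no further patients will be enrolled from the histology in which no patients met the" endpoint in stage 1. The synopsis repeats this.

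The stage 2 split is given separately, and its only condition is that stage 2 opens. The synopsis says "among the 24 patients subsequently enrolled, 12 patients will have LMS and 12 patients will have LPS". Section 15.1 says "among the 12 patients subsequently enrolled, 12 patients will have LMS and 12 patients will have LPS".

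Section 4.3 states "The study size is 34 patients", with no exception for the branch. Section 15.2 says that "accrual is expected to be complete in no more than 17 months".

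**The concern.** In the branch, the plan requires 12 more patients of a histology that it has just closed. The two instructions cannot both be followed, and the text does not say which gives way. The phrase full accrual has no number attached, so two readings are open:

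- All 24 remaining places go to the retained histology (34 in total).
- Only that histology's own quota of 12 is filled (22 in total).

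A third reading, 34 patients of the retained histology, would give 39 overall and contradict the stated total.

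The same stage 1 data could therefore lead to different trial sizes and very different chances of reaching 15 successes. The conclusion is also worded for the agent as a whole, although in this branch the closed histology would have had 0 successes in 5. Separately, the sentence in section 15.1 that sets the split contradicts itself, because 12 + 12 is 24, not 12.

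**Working it through.** **Inputs (section 15.1).** Stage 1: 5 + 5 patients, continue with at least 4 successes. Stage 2: 24 more. Final bar: 15 successes. Rates: 30% and 55%. All probabilities are exact binomial and assume that all patients are evaluable.

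**The plan's own figures.** P(success) = sum over x = 4 to 10 of P(Bin(10, p) = x) × P(Bin(24, p) ≥ 15 − x).

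- p = 0.30: 0.0456, within the stated 0.05.
- p = 0.55: 0.8532, matching the stated 85%.

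**How often the branch is entered.** It needs 4 or 5 successes of 5 in one histology and 0 of 5 in the other.

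- Both at 30%: 2 × (0.02835 + 0.00243) × 0.16807 = 0.0103.
- Both at 55%: 2 × (0.20589 + 0.05033) × 0.01845 = 0.0095.
- One at 55%, the other at 30%: (0.20589 + 0.05033) × 0.16807 + (0.02835 + 0.00243) × 0.01845 = 0.0431 + 0.0006 = 0.0436. This split of the plan's two rates is an assumption.

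**Success once in the branch, keeping the bar of 15.** The retained histology brings 4 or 5 successes, so it needs 11 or 10 more. With m further patients, the chance is the average of P(Bin(m, p) ≥ 11) and P(Bin(m, p) ≥ 10), weighted by the probabilities of 4 and 5 successes. At 55% the weights are 0.804 and 0.196; at 30% they are 0.921 and 0.079.

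| Further patients | Total | At true 30% | At true 55% |
|---|---|---|---|
| 12 | 22 | 0.00003 | 0.804 × 0.0083 + 0.196 × 0.0421 = 0.015 |
| 24 | 34 | 0.921 × 0.0742 + 0.079 × 0.1528 = 0.080 | 0.804 × 0.8659 + 0.196 × 0.9352 = 0.880 |
| 29 | 39 | 0.240 | 0.982 |

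**Effect on the whole trial, bar of 15 throughout.**

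| Further patients in the branch | Both 30% | Both 55% | 55%/30% |
|---|---|---|---|
| 12 | 0.0448 | 0.8450 | 0.3968 |
| 24 | 0.0456 | 0.8532 | 0.4340 |
| 29 | 0.0473 | 0.8542 | 0.4385 |

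**What 15 means in the branch.** The closed histology contributes no successes, so 15/34 is in effect 15 of 5 + 24 = 29 in the retained histology: 52%, against 44% for 15/34.

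**Accrual.** Seventeen months is 34/2, the slowest planned rate. If the histologies recruit equally (an assumption), the retained one supplies 1 to 1.5 patients per month and 24 patients take 16 to 24 months. Adding stage 1 (10/3 to 10/2 = 3.3 to 5 months) gives about 19 to 29 months. Staying within 17 months would need the retained histology to supply 24/((17 − 3.3) × 3) = 59% of accrual at 3 per month, or 24/((17 − 5) × 2) = 100% at 2 per month.

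**The case against.** The strongest reply is that a specific exception displaces a general rule. Nobody would enroll into a histology that the same section has closed, and with a total of 34 stated repeatedly and without exception, full accrual most plainly means 34. The 15/34 rule for the overall population then still applies, with the five closed-histology patients in the denominator. This largely stands. Size and cut-off can be read from the documents, so a reader who inferred that the branch has no sample size or decision rule at all would go too far. What remains is that the text never says the split lapses, and that it does not narrow the conclusion.

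A second reply is that the branch is rare and that section 15.1 reports similar outcomes in LPS and LMS in a subset analysis of the trabectedin trial. This also stands. Higher entry rates need one histology to do much worse than 30%, and the documents give no such rate.

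A third reply is that keeping 15 successes while narrowing the conclusion sets a stricter bar. As a plain single-stage rule, 15/29 has type 1 error 0.012 and power 0.707. That is fair. The 8% and 88% figures apply only after at least 4 of 5 successes have been seen, and they should be labelled so.

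**Conclusion.** The inconsistency and the misprint are real, and the point is minor. A reader might infer that the stated 85% power and 0.05 type 1 error are wrong. They are not: under the natural reading they are 0.853 and 0.0456, and the other readings move them by less than one percentage point when both histologies share a rate.

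The consequence is confined to the branch, which is entered about 1% of the time at equal rates and 4.4% at the assumed 55%/30% split. There, at a true 55%, the reading changes the chance of success from 88% (24 more) to 1.5% (12 more, with 15 still required). The plan sets no other cut-off for 22 patients.

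Two further inferences are not supported. At least 4 of 5 uncontrolled patients progression-free at 12 weeks would not show benefit in the retained histology. Nor is it established that accrual would overrun 17 months, since that depends on how recruitment splits between the histologies, which the documents do not give.

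**What to change.** In the synopsis and section 15.1:

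1. Correct the stage 2 total in the section 15.1 allocation sentence from 12 to 24. The synopsis already has 24.
2. State that the 12 + 12 split applies only while both histologies stay open, and that otherwise all 24 stage 2 patients come from the retained histology, for 34 in total.
3. State that 15 or more successes are still required, in effect 15/29 in the retained histology. Add that, once in the branch, the chance of success is about 8% at a true 30% and 88% at 55%.
4. Limit a positive conclusion in this branch to the retained histology.

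In section 15.2, say that accrual in this branch may exceed 17 months, depending on how recruitment splits between the histologies.

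The cost is a few sentences and one corrected number, with no patients beyond 34. The edit should be made before the stage 1 interim analysis, so that the reading is not chosen with the data in view. The only cost in conduct is possible extra accrual time if the branch occurs.
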